In addition to circadian rhythm and HPA regulatory systems, emerging evidence suggests that the autonomic nervous system is implicated in the development of insomnia among cancer patients.⁴¹ Falling asleep involves a neurophysiological switch from predominantly sympathetic to parasympathetic tone.⁴² Our data showed that cancer patients who have insomnia also have attenuated parasympathetic tone as measured by respiratory sinus arrhythmia (RSA).⁴³ RSA measures the variation of heart rate with respiration and changes in

heart rate and can be used as a proxy measurement of general parasympathetic tone.⁴⁴ The parasympathetic nervous system (PNS) is influenced by the circadian system, while the sympathetic nervous system is influenced by the sleep-wake system.⁴⁵ The suprachiasmatic nucleus (SCN) is a master circadian clock, which regulates autonomic and HPA function through endocrine modulation. Emerging evidence in both healthy people and cancer patients suggests that circadian rhythms and the autonomic nervous system are dysregulated in those with sleep problems via multiple photo (e.g., light exposure) and non-photo sensitizers (e.g., cancer treatments, physical activity). In cancer patients and survivors, circadian rhythm disruption,

Behavioral Intervention for Insomnia in Cancer

autonomic dysfunction and sleep problems are prevalent (Figure 1).^{3,8,9,43,46} However, no studies known to the authors have examined all three systems and attempted to intervene. Understanding the nature of the relationship between sleep problems, circadian rhythm and autonomic nervous system activity is of considerable clinical and research interest in cancer, because it may lead to the development of new therapeutic approaches. Treating insomnia in patients may improve quality of life and overall health by normalizing circadian rhythms and autonomic tone.

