5. INVESTIGATIONAL PROCEDURE INFORMATION

5.1 Investigational Procedure

BBT-I Intervention Group: 90 BC patients will be randomized to receive the BBT-I. BBT-I includes both stimulus control and sleep scheduling, however it has been modified from CBT-I to make it more suitable for cancer patients undergoing chemotherapy with recently developed sleep problems. The main intervention component is one face-to-face 60-minute session with a trained staff member during which time an individually tailored “sleep prescription” is developed. There will also be four 15-minute phone calls and a second 60-minute face-to-face “booster” session. The second face-to-face session will ideally occur during the third or fourth week depending on the patient’s chemotherapy regimen.

BBT-I is a novel intervention that applies innovative cancer-specific chronorehabilitation techniques to effectively treat acute insomnia among patients receiving chemotherapy in the infusion clinic. It is comprised of the following four components: 1) **chronorehabilitation education** (e.g., information on the contribution of circadian disruption to insomnia in the context of cancer and cancer treatment, a review of the cancer-specific behavioral model of insomnia, and discussion regarding how insomnia and fatigue may co-occur and interact.); 2) **light and stimulus control** (e.g., decrease light exposure at night and increase light exposure during the day, do not go to bed until sleepy, and get out of bed if not sleeping); 3) **encouragement of physical activity and discouragement of napping** (e.g., increase exercise and limit naps to 2 per day and no longer than 45 minutes); and 4) **sleep compression** (e.g. increasing motivation to regulate sleep and wake cycles, and go to bed later by at least 15 minutes if sleep efficiency is less than 85%). Patients are told that on their sick days (e.g., days post chemotherapy) they can nap and sleep as much as they need to. In our pilot, we found that patients successfully moderated their sleep prescription on the days when they were not feeling well.

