Healthy Eating Education Learning (HEAL) control group: 90 BC patients will be randomized to receive HEAL. HEAL will control for attention and provide a behavioral “placebo.” This control condition will consist of 2 face-to-face sessions and 4 phone calls. The content of the intervention is provided by the NCI: PDQ® Nutrition in Cancer Care. The topics will include nutritional implications of chemotherapy, nutrition screening and assessment, and nutritional suggestions for symptom management (e.g., nausea). To improve the credibility of HEAL

Behavioral Intervention for Insomnia in Cancer

intervention for sleep; the therapists will discuss the connection between healthy eating and good sleep. We expect this to be an aspect of intervention that should bolster the credibility of the control condition as there are sound reasons to think that nutrition could have some effect on insomnia. Nevertheless, we anticipate the effects of HEAL on insomnia would be weak given the evidence behind behaviors that influence sleep which are not targeted by HEAL. In addition, the healthy eating education control has successfully been used as an attention control group for sleep intervention during chemotherapy.^{52,59}

For clinicaltrials.gov and Stanford Clinical Trials Directory compliance

Intervention Description

Women diagnosed with breast cancer receiving chemotherapy will be randomized to either Brief Behavioral Therapy for Insomnia (BBT-I) or Healthy Eating Education Learning (HEAL) control group. BBT-I is a novel intervention that combines chronorehabilitation and cognitive behavioral therapy for insomnia (CBT-I) techniques that are specifically adapted for women diagnosed with breast cancer who are undergoing treatment. Patients randomized to BBT-I will receive 2 face-to-face sessions and 4 phone calls. The control group is patterned after the control group used in a large RCT^{52,53}. HEAL will control for the non-specific components of time, attention, and health education that are not specifically related to sleep management. The control treatment will involve 2 face-to-face sessions and 4 phone calls exactly like BBT-I.

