Physiological Mediators Heart Rate Variability (HRV) will be calculated with the ambulatory monitoring heart-rate device Firstbeat® that measures RR intervals with a rating sample of 1ms. The device utilizes a valid and reliable method for sampling RR intervals and provides software to analyze the raw data.⁷⁶⁻⁷⁸ We will calculate time and frequency domain measures of HRV: SDNN, (the standard deviation of all normal RR intervals measured between consecutive sinus beats) and RMSSD (the root mean square of successive differences between adjacent normal R-R intervals).^{76,79} In addition, we will measure frequency domain measures, natural log of high frequency (HF, total spectrum power of all NN intervals between 0.15 to 0.4Hz) for vagal tone/RSA and natural log of low frequency (LF, total spectrum power of all NN intervals between 0.04 to 0.15Hz) and LF/HF ratio. Given our preliminary data in BC patients, we will use RSA as a primary HRV outcome. Heart rate variability data will not be collected from a participant if she has an implanted device for heart failure (e.g., pacemaker, defibrillator, left ventricular assist device, etc.).

Circadian Rhythm will be assessed using actigraphy and salivary cortisol at each of the 4 assessment points (sleep diaries are used for cross-checking the going to sleep and waking up times). A two-oscillator cosinor model (12 and 24 hours) will be calculated using nonlinear regression methods on the log (activity counts). This model was found to fit the data for cancer survivors⁸⁰ better than a single-oscillator model. Mesor (overall), Amplitude, and Acrophase for the 12- and 24-hour cycles will be calculated. In addition, we will collect salivary cortisol per modified McArthur protocol⁸¹ for 2 days at wake, wake +30, 12PM, 5PM and before bedtime (baseline, 6-, 30-, and 58-weeks). Saliva samples will be refrigerated after collection and stored at -70 °C within a couple of days of collection. Samples will be assayed using a luminescence immunoassay (Immuno-Biological Laboratories Inc, Germany) at Stanford Labs.

Reduced Horne Ostberg Morning Evening Questionnaire (rMEQ) will determine the chronotype of the participant to help assess activity of various physical functions. This questionnaire is a shortened version of the Horne-Ostberg Morning Eveningness Questionnaire.⁸² It is a seven-item questionnaire that asks various questions of daily choices regarding sleep and other activities.

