The dysfunctional beliefs about sleep will be measured utilizing the Dysfunctional Beliefs and Attitudes about Sleep Scale,⁸⁶ a self-report measure that was designed to examine changes in erroneous sleep beliefs and attitudes. Potential moderators will be assessed using age, baseline anxiety and depression (Clinical Assessment of Depression), hot flashes (daily diary), caregiver status (questionnaire), as well as emotional regulation (Difficulties in Emotion Regulation Symptoms). The Nutrition Knowledge Questionnaire (NKQ) will also be used to control for attention.

The Difficulties in Emotion Regulation Scale (DERS)⁸⁷ will be used to determine emotion regulation. The DERS is a brief, 36-item, self-report questionnaire devised to assess several aspects of emotion dysregulation. The measure yields a total score as well as scores on six scales produced through factor analysis: Nonacceptance of emotional responses (NONACCEPTANCE), difficulties engaging in goal directed behavior (GOALS), impulse control difficulties (IMPULSE), lack of emotional awareness (AWARENESS), limited access to emotion regulation strategies (STRATEGIES), and lack of emotional clarity (CLARITY). This measure has been found to have high internal consistency, good test–retest reliability, and adequate construct and predictive validity.

Other variables. We will extract the following medical variables from the patients’ medical records: disease stage, chemotherapy type (e.g., doxorubicin), prior treatment (e.g., surgery), and receptor status. We will record the treatment that the patient is on during each assessment point to account for differences that might be associated with their particular treatment regimen. We will also determine exercise and physical activity through the Godin Leisure Time Exercise Questionnaire (GLTEQ). The GLTEQ is a 4-item test that asks the frequency of strenuous, moderate and mild exercise. It has been validated to examine changes of behavior in activity.⁸⁸ The NKQ will be given to enhance the validity of the control intervention. It is a 15-item questionnaire that measures competency of nutrition.

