12.5 Secondary Analysis

Aim 2 (Secondary): To evaluate efficacy of the BBT-I in treating cancer-related symptoms such as cancer-related fatigue and cognitive difficulties in breast cancer patients receiving chemotherapy.

Hypothesis 2 (Secondary): BBT-I compared to an attention control group will be associated with greater improvements in fatigue and cognitive difficulties (as measured by the Brief Fatigue Inventory, and our Cognitive Battery that includes neuropsychological testing) from baseline through the 12 month follow up.

Aim 3 (Secondary): To examine potential moderators and mediators of BBT-I intervention effects on insomnia, cognitive difficulties, and fatigue. In particular, we are interested in age, depression and anxiety, emotion regulation and side effects (hot flashes) as potential moderators of the intervention effects as well as evaluating modifiable behavioral and physiological mechanisms as hypothesized mediators.

Hypothesis 3 (Secondary): In women with breast cancer receiving chemotherapy, intervention effects on insomnia, fatigue, and cognitive difficulties will be mediated by select behavioral mechanisms [i.e., maladaptive sleep behaviors (The Sleep Behavior Self-Rating Scale, sleep diaries, actigraphy), dysfunctional beliefs and attitudes (Dysfunctional Beliefs and Attitudes about Sleep) and physiological mechanisms [i.e., dysregulated circadian rhythms (measured by salivary cortisol), disrupted sleep wake cycles (actigraphy), and autonomic tone (RSA)].

As hypothesized mediators, we will carefully examine behavioral (measured by DBAS, SBSRS and sleep diaries) and physiological mechanisms (measured by HRV, salivary cortisol and actigraphy). Examination of moderators will be exploratory. As potential moderators, we will examine age, baseline anxiety and depression, baseline emotion regulation and baseline hot flashes. Among these potential moderators, some will not be qualified as moderators but predict outcome regardless of the intervention assignment status (we will classify these as non-specific predictors of the outcome). For the moderator/mediator investigation, we will apply the McArthur framework.^{98,99} Our analysis strategy in detecting moderators and mediators is mixed effects modeling, where the McArthur approach will be embedded.

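### BBT-I tells patients to exercise more and exercise is measured at every assessment, but it is missing from the Hypothesis 3 mediators, so an exercise effect could be read as a rest-activity or circadian mechanism

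*Combined protocol and SAP*

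**What the plan says.** - **Intervention.** Section 5.1 gives the third of BBT-I's four components as "encouragement of physical activity and discouragement of napping", with the example "increase exercise and limit naps to 2 per day and no longer than 45 minutes". HEAL is described there as nutrition education. The section expects it to have little effect on insomnia, given "the evidence behind behaviors that influence sleep which are not targeted by HEAL".
- **Rationale.** Section 2.3 lists, among the influences through which the circadian and autonomic systems become dysregulated, "non-photo sensitizers (e.g., cancer treatments, physical activity". It also says that the trial will concentrate on two physiological mechanisms, the circadian pattern of activity and HRV.
- **Mediators.** Hypothesis 3 in Section 12.5 names the behavioural mediators as "maladaptive sleep behaviors (The Sleep Behavior Self-Rating Scale, sleep diaries, actigraphy), dysfunctional beliefs and attitudes" and the physiological ones as "dysregulated circadian rhythms (measured by salivary cortisol), disrupted sleep wake cycles (actigraphy), and autonomic tone (RSA". The instrument lists in Sections 12.3 and 12.5 are DBAS, SBSRS and diaries on one side, and HRV, cortisol and actigraphy on the other.
- **Rhythm measure.** Section 10.1, under Physiological Mediators, assesses circadian rhythm by actigraphy together with cortisol. For the actigraphy it states: "A two-oscillator cosinor model (12 and 24 hours) will be calculated using nonlinear regression methods on the log (activity counts". Mesor, amplitude and acrophase come from that fit.
- **Exercise measure.** Section 10.1, under Other variables, says: "We will also determine exercise and physical activity through the Godin Leisure Time Exercise Questionnaire (GLTEQ". The Section 9 calendar has it at baseline, post-intervention, 6 and 12 months. No analysis uses its change over time. The covariate sensitivity analysis in Section 10.1 concerns baseline variables only.
- **Power.** Section 12.6.2 bases power for Hypothesis 3 on the mediator-outcome association (r = 0.2 to 0.3, stated power 0.76 to 0.99), with no adjustment for testing several mediators.

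**The concern.** Randomisation protects the comparison of arms on the mediator and on the outcome. It does not protect the association between mediator and outcome, which is the path that the plan powers and tests. Exercise is something that one arm is told to change. By the protocol's own rationale it is connected to the circadian and autonomic systems, and it enters the activity counts directly. If it also affects insomnia, fatigue or cognition by another route, then a mediator that merely moves with exercise can appear to carry the treatment effect.

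What is at stake is the mechanistic conclusion. Section 2.3 presents the trial as a way to understand the role of circadian and autonomic regulation in insomnia. With exercise outside the mediator models, the planned analysis has no means of showing how far an actigraphy-based mediation result depends on patients simply moving more.

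**Working it through.** **1. The plan's own figure.** Inputs from Section 12.6.2: r = 0.2 and 0.3, two-sided alpha 0.05, N = 180. Fisher z power is Φ(atanh(r) × √(N − 3) − 1.96).
- r = 0.2: 0.2027 × 13.304 − 1.96 = 0.737, power 0.770.
- r = 0.3: 0.3095 × 13.304 − 1.96 = 2.158, power 0.985.

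The stated 0.76 to 0.99 therefore reproduces, if all 180 patients contribute. At the plan's 25% attrition (180 × 0.75 = 135) the same formula gives 0.644 and 0.945. One added covariate replaces N − 3 by N − 4 and gives 0.767 and 0.984 at N = 180, with r read as a partial correlation.

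**2. What extra movement does to mesor and amplitude.** Assumptions, not in the documents: 16 h awake, 8 h asleep, a square activity profile, and 20% more daytime counts at unchanged clock times.

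Spread evenly over the waking day:
- Rise in log counts: ln(1.2) = 0.182.
- Mesor: 0.182 × 16/24 = 0.12.
- 24-hour amplitude: (2/π) × sin(π × 16/24) × 0.182 = 0.551 × 0.182 = 0.10.
- Acrophase does not move, because the profile stays symmetric about the same midpoint.

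The same extra counts in one 30-minute bout:
- Multiplier in the bout: 1 + (0.2 × 16)/0.5 = 7.4, and ln(7.4) = 2.00.
- Mesor: 2.00 × 0.5/24 = 0.042, about a third of the first value.
- 24-hour amplitude, bout at the midpoint of the waking day: (2/π) × sin(π × 0.5/24) × 2.00 = 0.0416 × 2.00 = 0.083. A bout 4 h from the midpoint gives, to first order, 0.083 × cos 60° = 0.042, and it also moves the acrophase.

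In these profiles the mesor and amplitude rise with no change in sleep. Whether 0.04 to 0.12 log units is large cannot be judged, because the plan gives no SD.

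**3. How often this could produce a mediation finding.** Simulation, 2,000 trials per setting, under assumptions that are not in the documents: treatment acts on the outcome only through exercise (treatment effect on exercise d = 0.4 to 0.6); the activity-count mediator has no effect of its own; the exercise-mediator correlation is 0.3 to 0.7; the exercise-outcome correlation is 0.2 to 0.3. The induced mediator-outcome correlation is then the product, 0.3 × 0.2 = 0.06 up to 0.7 × 0.3 = 0.21.

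| N = 180 | Share of trials significant |
|---|---|
| Mediator-outcome test, exercise omitted | about 12% to 82% |
| Both mediation paths, exercise omitted | about 2% to 66% |
| Mediator-outcome test, exercise included without error | about 5% |
| Mediator-outcome test, exercise included at assumed reliability 0.6 | about 5% to 28% |

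With 134 patients, close to the number left after 25% attrition, both paths are significant in about 1% to 46%.

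**4. Which mediators are exposed.** Mesor and amplitude are functions of activity counts, so the exposure is direct. RSA and cortisol are not computed from counts; Section 2.3 links physical activity to those systems but gives no size. DBAS and SBSRS are questionnaires, and nothing in the documents says that exercise shifts them.

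**The case against.** Five arguments deserve weight.

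- **Hypothesis 3 names cortisol.** A reader might infer that Hypothesis 3 measures circadian rhythm from activity counts. Its text does not: it assigns circadian rhythm to salivary cortisol, and actigraphy to sleep-wake cycles and sleep behaviours. This stands. It does not remove the problem, because actigraphy is still a listed physiological mediator and Section 10.1 fits the rhythm model to counts under that heading. The two sections need to be reconciled.
- **Exercise may be upstream.** If exercise improves rhythm or RSA, which then improves sleep, mediation by rhythm is real. Section 2.3 fits that reading, and the documents give no evidence of a separate route from exercise to outcome. This stands, and it limits what adjustment can show. GLTEQ and actigraphy are measured at the same assessment and both with error, so a mediation estimate that shrinks on adjustment could mean confounding by exercise or a genuine exercise-to-rhythm pathway.
- **The even 20% rise is favourable to the concern.** This is right for the mesor, which falls to 0.042 with a single bout. The amplitude is less sensitive when the bout is near midday (0.083).
- **Exercise is not the only candidate.** Napping and light exposure are also changed by BBT-I, and Hypothesis 3 claims only selected mechanisms. Fair. But exercise has its own validated instrument at every assessment, no analysis role, and a direct arithmetical link to one of the mediators.
- **HEAL's full content is not in the documents.** Correct. The statement here is only that its description includes no exercise content.

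Requiring a shift in acrophase before any circadian claim looks like a tempting safeguard. It would not work: Section 5.1 also has BBT-I patients change bedtime and light exposure, so acrophase fitted to counts can move by instruction too.

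**Conclusion.** The gap is real. Exercise is an instructed ingredient of one arm, is measured at every assessment, and is absent from every mediator list, while one listed mediator is built from activity counts. An exercise effect could therefore be read as a rest-activity or circadian mechanism. The risk is most direct for mesor and amplitude, and weaker for RSA and cortisol.

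A reader might go further and infer that an exercise effect would be reported as a circadian mechanism, or that the data cannot bear on the question at all. The documents do not support that. The range of about 2% to 66% rests entirely on assumed correlations and an assumed exercise-only mechanism, and its lower end is small. Cortisol, which Hypothesis 3 names for circadian rhythm, is not derived from counts.

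The consequence is confined to the interpretation of a secondary hypothesis. The randomised comparisons in Hypotheses 1 and 2 are unaffected. The change is still worth making, because it uses data already collected and bears directly on what Hypothesis 3 can conclude.

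**What to change.** In Sections 12.3 and 12.5:

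1. Pre-specify change in GLTEQ from baseline to week 6 as a candidate behavioural mediator for insomnia, fatigue and cognition.
2. Report the mediation results for the actigraphic rhythm, RSA and cortisol with and without GLTEQ change, and say in which model (treatment to mediator, mediator to outcome, or both) it enters.
3. State in advance that attenuation on adjustment does not distinguish confounding by exercise from a pathway that runs from exercise through rhythm.
4. Label mesor and amplitude as rest-activity measures.
5. Reconcile Section 10.1 (circadian rhythm by actigraphy and cortisol) with Hypothesis 3 (by cortisol), so that one definition applies.

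The cost is plan wording and a few extra model fits, with no new data. Power for the mediator path barely changes from the added covariate itself (0.770 to 0.767 at r = 0.2, N = 180, if r is read as a partial correlation). Mediation estimates may become smaller or less precise where exercise and the mediator overlap. Adjustment will be incomplete, because the GLTEQ is a four-item self-report: at an assumed reliability of 0.6, the false mediator-outcome rate in the simulation was still about 5% to 28%.

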Telomeres are repeated regions of DNA at the ends of chromosomes that primarily serve to protect against loss of integral DNA sequence during DNA replication. However, the length of telomeres shorten with time and repeated cell replication, and studies have shown that telomere shortening often correlates with early mortality, lifetime depression exposure, psychological stress, oxidative stress, and increased risk for certain types of cancer. To date, the link between telomere shortening and sleep disruption or maintenance has not been fully explored. Because there is circumstantial evidence linking telomere shortening to Obstructive Sleep Apnea Syndrome, exploring the correlation between the length of telomere and sleep may uncover a novel way to both diagnose and treat sleep disruption in patients. Thus, measurement of telomere length can help explain presence of sleep disturbance. In addition, gene expression in relation to insomnia in cancer may be explored if additional funds or collaborations develop.

Preliminary Data

Pathophysiology of sleep problems in cancer. In our pathophysiologic study (Paresh et al.)⁴³ in women with metastatic BC, sleep was assessed by means of questionnaires and wrist actigraphy. Vagal regulation was assessed via respiratory sinus arrhythmia (RSA_{TF}). Longer nocturnal wake episodes were significantly associated with a flatter diurnal cortisol slope. Sleep problems were also associated with diminished RSA. Higher RSA was significantly related to higher sleep efficiency and a correspondingly lower number of wake episodes and lower waking after sleep onset (WASO), and lower average length of nocturnal wake episodes. While demographics, disease severity, and psychological variables all explained some portion of the development of sleep problems, 4 of the 6 sleep parameters examined (sleep efficiency, WASO, mean number of waking episodes, average length of waking episode) were best explained by RSA. These data provide evidence for an association between disrupted nocturnal sleep and reduced RSA the following day. They suggest that the stress-buffering effects of sleep may be associated with improved parasympathetic tone and normalized circadian rhythmicity as evidenced by cortisol patterns during the day and greater RSA.

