Expectancy/Feedback will be obtained by 2 checklists assessing the usefulness and acceptability of the experimental interventions and intervention outcome expectancy. Participants will complete the expectancy checklist at the end of their first face-to face session and feedback questionnaire at post-intervention to assess whether they found our interventions helpful for their symptoms. For these baseline variables that are not considered as potential moderators, given our strong design based on random assignment to treatment and control groups, it is reasonable to assume that they will be balanced between the intervention and control groups (i.e., no need to worry about controlling for them). Nonetheless, we will test sensitivity of our results to presence/absence of these potential baseline covariates, especially those that differ between groups due to natural experimental error.

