12.6.2 Sample size justification

For the primary Hypothesis 1 (BBT-I will show greater reduction of insomnia symptoms measured by ISI from baseline to the 12-month follow-up compared to the control), we estimated power in the proposed mixed effects modeling framework fully accounting for the longitudinal study design and projected attrition rate. The primary outcomes, ISI, will be measured at baseline, 6 weeks (end of treatment), 30 weeks, and 58 weeks (primary end point). For our power estimation, we used ML based mixed effects modeling assuming a linear trend. We assumed that at least 60% of variance is explained by the growth model for the primary outcome (i.e., reliability of 0.6), given that previous studies reported reliability ranging from 0.65-0.83.^{105,106} For attrition, we assumed gradually increasing attrition over time, resulting in 25% attrition by the 6-month follow-up assessment. We assumed a medium effect size, Cohen's d of 0.4 to 0.6, based on a previous study.¹⁰⁷ We also consider this range of effect size as the lower bound of a clinically meaningful treatment effect. Under this scenario, the estimated power to detect the group difference in change in ISI is 0.88-0.99 ($d=0.4$ to 0.6 , $\alpha=.05$, two-tailed) with $N=180$ (90 BBT-I, 90 control). We estimated power for the secondary Hypothesis 2 (BBT-I compared to the control will show greater improvements in fatigue and cognitive difficulties) using the same mixed effects modeling strategy. We assumed a moderate effect size of $d = 0.35$ to 0.4 , based on a previous study.^{108,109} We do not adjust for testing of multiple outcomes given that fatigue and cognitive difficulties are secondary outcomes. Under this scenario with reported reliability of 0.67 and higher,^{108,109} the estimated power to detect the group difference in change in BFI is 0.84-0.91 ($d=0.35$ to 0.4 , $\alpha=.05$, 2-tailed). For the mediator Hypothesis 3, we estimated power focusing on the main effect of the mediator on the outcome.^{98,99} We assumed a

Behavioral Intervention for Insomnia in Cancer

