moderate correlation between the hypothesized mediators and the outcome ($r=0.2$ to 0.3). We do not adjust for testing of multiple mediators given our concerns in failing to detect possible mediators due to insufficient power (note that our trial is powered based on our primary hypothesis). Under this scenario, the estimated power to detect the mediation effect is $0.76-0.99$ ($r=0.2$ to 0.3 , $\alpha=.05$, two-tailed). For all hypotheses, we will carefully monitor both statistical (i.e., p-value) and clinical (i.e., effect size) significance, with more emphasis on clinical significance in the secondary hypotheses.

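### Hypothesis 3 infers mediation from a mediator–outcome association that randomisation does not protect, and section 12 names no adjustment for common causes, so a confounded marker could be reported as a mechanism

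*Combined protocol and SAP*

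**What the plan says.** Section 12.5 states Hypothesis 3 in causal terms: "intervention effects on insomnia, fatigue, and cognitive difficulties will be mediated by select behavioral mechanisms", and also by physiological ones (salivary cortisol, actigraphy, RSA). The method is one sentence, repeated in substance in section 12.3: "Our analysis strategy in detecting moderators and mediators is mixed effects modeling, where the McArthur approach will be embedded". Neither section gives a model equation, a covariate list, an assumption about confounding, or a sensitivity analysis for it.

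Section 12.6.2 shows which quantity is tested: "we estimated power focusing on the main effect of the mediator on the outcome". It assumes a "moderate correlation between the hypothesized mediators and the outcome" of 0.2 to 0.3, gives power of 0.76 to 0.99 at a two-sided alpha of 0.05, and makes no adjustment for testing several mediators.

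Four other places bear on the point:

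- **Section 10.1, Expectancy/Feedback paragraph.** Baseline variables that are not potential moderators are expected to be balanced by random assignment, so there is "no need to worry about controlling for them". The paragraph then promises to compare results with and without these covariates, with emphasis on those that differ between arms.
- **Section 10.1, Other variables paragraph.** "We will record the treatment that the patient is on during each assessment point to account for differences" linked to the regimen. No model in section 12 takes this up.
- **Section 4, Procedures paragraph.** Saliva collection is timed ahead of chemotherapy appointments to keep corticosteroids from affecting cortisol.
- **Section 12.5.1.** The sensitivity analyses concern missing data, and the hypotheses named are 1 and 2.

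**The concern.** A claim of mediation needs two links: arm to mediator, and mediator to outcome. Randomisation protects the arm-to-mediator link. It does not protect the other, because women are assigned to BBT-I or HEAL and not to levels of DBAS, SBSRS, RSA, cortisol or activity rhythm. Anything that drives both the mediator and the outcome within an arm produces an association between them even if the mediator does nothing.

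Balance between arms is therefore the wrong criterion here. A variable with identical distributions in both arms can still confound the mediator–outcome link.

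The documents give reason to expect such variables. Section 2.5 reports, in earlier work by the team, that "demographics, disease severity, and psychological variables all explained some portion of the development of sleep problems". Section 2.3 describes depression and insomnia as closely related, and names cancer treatment among the factors that disturb circadian and autonomic function.

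At stake is the mechanistic conclusion for insomnia, fatigue and cognition. If BBT-I shifts a marker at all, a shared cause could supply the rest of the evidence for calling it a mediator.

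**Working it through.** **Inputs from the documents:** N = 180 (section 12.6.2); two-sided alpha 0.05; r = 0.2 to 0.3 and stated power 0.76 to 0.99 (section 12.6.2); 25% attrition by the 6-month assessment (section 12.6.2), so 180 × 0.75 = 135.

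**1. The plan's own figure.** Fisher z power for one correlation is Φ(atanh(r)·√(N−3) − 1.96), plus a second tail that is negligible here.

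- r = 0.2, N = 180: 0.2027 × 13.304 = 2.697; Φ(0.737) = 0.770.
- r = 0.3, N = 180: 0.3095 × 13.304 = 4.118; Φ(2.158) = 0.985.

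These agree with 0.76 and 0.99 to within two percentage points. The stated power is what a plain correlation test gives with all 180 women and no covariates. At N = 135 the same formula gives 0.644 and 0.945.

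**2. What a common cause alone can produce.** Assumption, not in the documents: one common cause has correlation a with both mediator and outcome, and the mediator has no effect on the outcome. The unadjusted mediator–outcome correlation is then a × a. Putting this into the same formula (both tails) gives the chance of a significant result:

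| a | Induced r | N = 180 | N = 135 |
|---|---|---|---|
| 0.1 | 0.01 | 0.052 | 0.052 |
| 0.2 | 0.04 | 0.083 | 0.075 |
| 0.3 | 0.09 | 0.225 | 0.179 |
| 0.4 | 0.16 | 0.574 | 0.458 |
| 0.5 | 0.25 | 0.925 | 0.835 |

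Unrounded, the N = 180 values for a = 0.3 and 0.5 lie just below those shown, at about 22% and 92%. The induced correlation reaches the plan's target range of 0.2 to 0.3 when a is about 0.45 (0.45² = 0.2025) to 0.55 (0.55² = 0.3025).

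**3. Requiring both links.** A simulation (6,000 runs per setting) also required a significant effect of arm on the mediator. Further assumptions: BBT-I moves the mediator by 0.5 SD and the outcome directly by 0.4 SD, with no true mediation. At N = 180 both tests were significant in 4% of runs with no confounding, 21% at a = 0.3, 71% at a = 0.45 and 90% at a = 0.55. Adding the common cause to the outcome model returned the mediator–outcome error rate to about 5% and the mediator coefficient to about zero.

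**4. What the existing safeguards cover.**

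- The with-and-without check in section 10.1 is limited to baseline variables that are not moderators. Age, baseline depression and anxiety, hot flashes and emotion regulation are all moderators (sections 10.1 and 12.5), so these candidates fall outside it.
- The check stresses arm imbalance, and it is confined to baseline, so treatment during follow-up is not covered.
- Treatment recorded at each visit is not assigned to any mediator model.
- The saliva timing deals with corticosteroids and cortisol only. It does nothing for DBAS, SBSRS, RSA or actigraphy.

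**The case against.** The strongest reply is that the plan is silent, not wrong. Three stronger readings are tempting, and the documents do not support them.

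- **That the mediator models will be unadjusted.** Sections 12.3 and 12.5 neither include nor exclude covariates. The power figure matches an unadjusted test, but that does not fix the final model.
- **That randomisation is offered as the justification for Hypothesis 3.** The sentence in section 10.1 is general, is not written for Hypothesis 3, and exempts the moderators. It therefore does not say that depression or age need no control. The check that follows stresses imbalanced variables without being restricted to them, and is not confined to Hypotheses 1 and 2.
- **That a false mechanism would be reported.** The documents give no confounder correlations. At 0.1 to 0.2 the error rate stays at about 5% to 8%.

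Further cautions are fair. The section 2.5 finding comes from women with metastatic disease, whereas this trial enrols Stage I–III, and it goes on to say that RSA best explained four of six sleep measures. The background ties depression, demographics and severity to sleep, not to a listed mediator; only cancer treatment is tied to both sides. The table treats a single cross-sectional correlation, while section 12.4.2 plans growth models of change, so the percentages need not carry over. What the McArthur framework itself requires is not described in the documents, and nothing here depends on it.

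These points limit the strength of the claim but do not remove the gap. No text assigns any adjustment to the mediator–outcome link, and the one stated principle for covariates uses a criterion that does not apply to it.

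**Conclusion.** The concern holds as a weakness in a secondary analysis. Hypothesis 3 makes a causal claim on a non-randomised link. Section 12 names no confounder set, no no-confounding assumption and no analysis of unmeasured confounding, and the safeguards elsewhere do not fill the gap. Followed as written, the plan could report a confounded marker as a mechanism.

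The size depends on confounder strength, which is assumed: from about 5% at a correlation of 0.1 to 92% at 0.5 for the mediator–outcome test at N = 180, against a nominal 5%. The primary between-arm comparison of ISI is unaffected. Without the change, positive Hypothesis 3 results support association and not mechanism.

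**What to change.** In section 12.5:

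- State that every Hypothesis 3 mediator–outcome model adjusts for arm, the baseline value of the mediator, the baseline value of the outcome, and a fixed list of common causes already collected: age, stage, baseline CAD, DERS and hot flashes, and cancer treatment at the visit. Make this adjustment whether or not the variables are balanced between arms.
- Specify how baseline outcome enters. In the planned growth model, baseline is one of the four repeated values, so it comes in through the intercept. Use it as a covariate only where the response is restricted to post-baseline values.
- State the assumption of no remaining mediator–outcome confounding, and add a sensitivity analysis giving the residual mediator–outcome correlation that would remove the mediated effect.

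In section 10.1, limit the randomisation argument to between-arm comparisons.

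The cost is SAP wording and somewhat larger models, with no new data. A few degrees of freedom are lost, and the estimated mediator effects may become smaller.
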